5.0 Registry Objectives

The primary objective of this registry is to evaluate the long-term safety of HUMIRA[®] in adult Ps patients who are treated as recommended in the product label. The secondary objective is to evaluate long-term effectiveness of HUMIRA[®] in adult Ps patients in the United States who are treated as recommended in the product label.

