If treatment with HUMIRA® is permanently discontinued for any reason, patients will be encouraged to remain in the registry. If a patient discontinues the registry, the physician will offer the patient participation in the direct to HCP Process, as applicable per local regulations, regardless of HUMIRA® treatment. Patients that have affirmatively

withdrawn their authorization to have their personal health information used or disclosed in connection with the registry will not be asked to continue in the registry or asked to participate in the HCP Process.

For patients who discontinue the registry, physicians will be asked to obtain the patient's signature on a Patient Authorization for Use/Disclosure of Data form for the completion of a simplified Healthcare Provider (HCP) questionnaire on an annual basis, as applicable per local regulations. The first data collection period will capture data from the date of the patient's discontinuation visit or last contact in the registry through the completion of the first annual HCP questionnaire for the patient. The questionnaire focuses on the collection of surgeries, hospitalizations, deaths, and the events listed as AEs of Special Interest (Table 2), AEs of Special Interest that lead to permanent discontinuation of HUMIRA®, and psoriasis related medication use since registry discontinuation. The questionnaire may be completed by the registry physician or the patient's current HCP (if they are no longer under the care of a registry physician). Any other SAEs experienced should be reported according to standard spontaneous reporting procedures, and they are not subject to the requirements of this protocol.

Effectiveness measures will not be collected from patients participating in direct to HCP Process.

All patients that are unreachable after three consecutive documented attempts to contact the patient via phone, email, or certified letter, will be considered lost to follow-up.

AbbVie will take reasonable actions to ascertain vital status at the end of the patient's 10-year observational period. AbbVie will make every effort to work through investigational sites to match patients lost to follow-up against the National Death Index (NDI) in the US, national/regional cancer registries and vital registries as available in other countries and as allowed per local regulations.

The registry procedures to be conducted in the registry are outlined in the schematic presented in Table 1.

[figure not shown]

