6.5.5 Physician's Global Assessment and Patient Reported Outcome Measurements

When applicable, information about the effectiveness of HUMIRA® therapy will be provided by the physicians and the patients. The Physician's Global Assessment (Appendix C) will be collected to assess the effectiveness of therapy at all registry visits at all sites. Effectiveness of therapy provided by the patient will be collected at US sites only utilizing patient reported outcomes (PROs) beginning at the enrollment visit and subsequently as outlined in Table 1. Effectiveness measures will be collected for patients participating in the registry regardless of HUMIRA® treatment. However effectiveness measures will not be collected as part of the HCP process. The PROs to be utilized include: Dermatology Life Quality Index (DLQI) (Appendix D), Patient Health Questionnaire PHQ-9 For Depression (PHQ-9) (Appendix E), Healthcare Resource Utilization (Unscheduled Outpatient Visits, Emergency Room Visits and Hospitalizations Questionnaire) (Appendix F), Work Productivity and Activity Impairment Questionnaire: Specific Health Problem V2.0 (WPAI:SHP) (Appendix G), Rosenberg Self-Esteem Scale (Appendix H, Census Socio-Demographic Questionnaire (Appendix I), Medical Outcomes (MOS)-Social Activities Scale (Appendix J), Psoriasis Impact and Experience (Appendix K), Illness Cognition Questionnaire (Appendix L), Insurance Status (Appendix M), and Patient Global Assessment (Appendix N).

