10.4 Effectiveness Analyses

Effectiveness parameters measured in this registry for patients enrolled in the US include: Physician's Global Assessment (PGA), Dermatology Life Quality Index (DLQI), Patient Health Questionnaire PHQ-9 For Depression (PHQ-9), Healthcare Resource Utilization, Work Productivity and Activity Impairment (WPAI:SHP), Rosenberg Self-Esteem Scale, Census Socio-Demographic Questionnaire, Medical Outcomes (MOS)-Social Activities Scale, Psoriasis Impact and Experience, Illness Cognition Questionnaire, Insurance Status, and Patient Global Assessment.

[figure not shown]
Descriptive statistics will be provided for the following variables according to the collection schedule outlined in Table 1:

- 1. PGA:
 - a. Proportion of patients achieving "clear."
 - b. Proportion of patients achieving "clear or minimal."
- 2. DLQI:
 - a. Proportion of patients achieving DLQI = 0.
 - b. Proportion of patients achieving DLQI = 0 or 1.
 - c. Change from baseline in DLQI.
- 3. PHQ9:
 - a. Change from baseline in PHQ9 total score.
- 4. Health Resource Utilization

- a. Proportion of subjects who had at least one event (e.g., hospitalization, ER, physician visits).
- b. Average number of events occurred per subjective who had at least one event.
- 5. WPAI-SHP: Change from baseline in the four impairment percentages:
 - a. Percent work time missed.
 - b. Percent impairment while working.
 - c. Percent impaired activity.
 - d. Percent overall work impairment.
- 6. Rosenberg Self-Esteem Scale: change from baseline in total score.
- 7. Census Socio-Demographic Variables: proportion of subjects in each category.
- 8. Medical Outcomes (MOS)-Social Activities Scale: change from baseline.
- 9. Psoriasis Impact and Experience: proportion of subjects who strongly agree, agree, not sure but probably agree, not sure but probably disagree or strongly disagree with any of the statements.
- 10. Illness Cognition Questionnaire: change from baseline in helplessness sub-score, acceptance sub-score and total score.
- 11. Insurance Status: proportion of subjects uninsured, or insured in any of the plan types.
- 12. Patient Global Assessment:
 - a. Proportion of patients achieving "Complete disease control."
 - b. Proportion of patients achieving "Complete disease control or good disease control."

Effectiveness data will be analyzed as observed, as this is an observational registry. Number of patients with non-missing baseline and visit values, baseline mean, visit mean,

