mean and standard deviation of change from baseline will be provided for continuous variables. Counts and percentages will be provided for categorical variables.

The effectiveness data will be summarized for the All Treated Patient Population (from the first dose in the registry) and the New Prescription Patient Population. For patients with TI, effectiveness summaries will combine data from all Treatment Periods, excluding the measurements from 14 days after the last dose during a treatment period up to the first dose in the subsequent Treatment Period.

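### Section 10.4 removes off-drug effectiveness data only before a restart, so assessments after a permanent stop are not excluded for patients without an earlier treatment interruption

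*Protocol*

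**What the plan says.** The aim is given in Section 5.0: "The secondary objective is to evaluate long-term effectiveness of" the drug in adult US patients treated according to the label.

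Follow-up and collection continue off drug. Section 6.5 says: "If treatment with HUMIRA® is permanently discontinued for any reason, patients will be encouraged to remain in the registry". Section 6.5.5 adds: "Effectiveness measures will be collected for patients participating in the registry regardless of HUMIRA® treatment". Collection stops only if the patient moves to the direct-to-HCP process.

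The analysis rules are in Section 10.4. "Effectiveness data will be analyzed as observed, as this is an observational registry". "The effectiveness data will be summarized for the All Treated Patient Population (from the first dose in the registry"), and also for the New Prescription Patient Population. No end of the window tied to the last dose is given. One off-drug rule follows, for patients with TI. Their data are pooled across every Treatment Period, with this one restriction: "excluding the measurements from 14 days after the last dose during a treatment period up to the first dose in the subsequent Treatment Period".

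Section 10.1 supplies the terms. A TI is a gap of more than 70 days without drug; it starts on day 71 after the last dose and runs to the day before the next first dose. A treatment period lasts until 70 days after its last dose.

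**The concern.** The exclusion shows that the authors want an on-drug summary: a patient who pauses and later restarts loses the assessments made in between. The rule needs a later treatment period to close the excluded interval. A patient who stops for good has none, so assessments made long after the last dose, on another psoriasis therapy or on none, can enter the same table as on-drug assessments.

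At stake is the interpretation of the secondary objective. As follow-up lengthens, more of the attending patients can be expected to have stopped. A trend across visits could then reflect the changing mix of on-drug, untreated and switched patients and be read as durability, or loss, of response.

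**Working it through.** The protocol states no figure for this point, so there is nothing to reproduce. The check sets the rules side by side and then illustrates the possible size.

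**Step 1: which records the text keeps.** Inputs are the window and exclusion in Section 10.4, the TI and treatment-period definitions in Section 10.1, and continued collection under Sections 6.5 and 6.5.5. Days are counted from the last dose before the gap or stop.

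| Patient | Up to day 14 | Days 14 to 70 | After day 70 |
|---|---|---|---|
| Pauses more than 70 days, then restarts | kept | excluded | excluded until restart |
| Had an earlier TI, now stops for good | kept | not excluded (no later period) | dropped, because data are pooled over Treatment Periods and the last one ends at day 70 |
| Stops once for good, no earlier TI | kept | not excluded | not excluded |

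The same off-drug time is thus handled in three ways. The third row carries the main problem; the second has a gap only between days 14 and 70.

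**Step 2: comparison within Section 10.** Exposure (Section 10.2) ends 14 days after the last dose. Treatment-emergent adverse events (Sections 10.3 and 10.3.2) end 70 days after it. Both close the final treatment period. Effectiveness has no corresponding closing cut.

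**Step 3: illustrative size.** Let p be the on-drug proportion clear or minimal on the Physician's Global Assessment, r the proportion among records after a permanent stop, and s the share of such records at a visit. Then

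reported proportion = (1 − s) × p + s × r, a shift of s × (r − p).

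None of p, r or s is in the protocol. Assume p = 60%:

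- s = 20%, r = 20%: 0.8 × 0.60 + 0.2 × 0.20 = 52%
- s = 20%, r = 70%: 0.8 × 0.60 + 0.2 × 0.70 = 62%
- s = 40%, r = 20%: 0.6 × 0.60 + 0.4 × 0.20 = 44%
- s = 40%, r = 70%: 0.6 × 0.60 + 0.4 × 0.70 = 64%

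A wider range, s = 50% with r from 10% to 80%, gives 35% to 70%. If r equals p, nothing changes. The direction depends on whether patients who stopped do worse (untreated) or better (switched successfully) than those still on drug.

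**The case against.** Several points can fairly be made against this.

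- **Retention is inferred.** No sentence says outright that data after a permanent stop are summarised. Section 6.5.5 governs collection, and the as-observed statement can be read as meaning only that nothing is imputed. This stands as a limit on certainty. But the window has a start, no end and one stated exclusion that does not reach these records; applied as written, it leaves them in.
- **The TI definition might cover permanent stops.** Its first sentence, a gap of more than 70 days, would do so if read alone. The next sentence ends the TI at a restart, and Section 10.4 uses the same end point, so this reading is not supported.
- **Not every permanent stop is affected alike.** A reader might infer that no off-drug data are excluded for anyone who stops for good. That is wrong for patients with an earlier TI, as the second row of the table shows.
- **The SAP may settle it.** It is not available, and it may. But the protocol does not leave the matter open: it sets an off-drug rule, and a SAP that follows that rule inherits the gap.
- **All data count in an observational registry.** A summary regardless of treatment would be legitimate. It would not then delete data from interruptions.
- **The stakes are limited.** Effectiveness is secondary and descriptive, with no test or sample-size dependence, and the primary safety analyses have their own cut-offs. Stoppers who move to the HCP process contribute no effectiveness data, which restrains s. All of this stands, and bears on priority rather than on whether the rule is right.

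**Conclusion.** The point holds in a bounded form. For patients without an earlier TI, the text does not exclude effectiveness records after a permanent stop. For patients with an earlier TI, the inconsistency is confined to days 14 to 70 after the final dose. The summary therefore answers neither the on-drug question nor the regardless-of-treatment question consistently.

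The conclusion rests on reading Sections 6.5, 6.5.5, 10.1 and 10.4 together. A reader might go further and infer that the protocol declares results on other therapies to be adalimumab effectiveness, or that the published figures will be biased by a known amount. The documents support neither: retention is a consequence of the rules rather than a stated intention, and the percentages above come entirely from assumed rates. What can be said is that the off-drug share can be expected to rise with time and that the bias may run in either direction. The correction should be made, but it concerns a secondary, descriptive objective.

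**What to change.** In Section 10.4, replace the TI-only exclusion with one rule for all patients: on-treatment effectiveness summaries use assessments from the first registry dose up to 14 days after the last dose of each Treatment Period, including the final one. Show assessments after the final window separately, labelled as after discontinuation.

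This needs a sentence and one additional display, using data the registry already collects, and it changes nothing in patient management. Late-visit samples become smaller, and the on-treatment summary describes patients who persist with the drug; the report should say so. If the sponsor would rather summarise everyone regardless of treatment, that is also coherent, provided data from interruptions are kept too and the table is labelled accordingly.

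A sensitivity summary counting patients who stopped for lack of effect as not clear or minimal is optional. It addresses selection of persisters, which is a different problem, and is not part of this correction.

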10.5 Interim Analyses

Interim reports are prepared on an annual basis and began in February 2010. Interim reports are submitted to Regulatory Agencies, as required.

10.6 Determination of Sample Size

The proposed sample size for this registry of a minimum of 5,000 patients is based on the lowest frequency AE of Special Interest (i.e., lymphoma) seen in HUMIRA [®] clinical trials.

According to the latest US National Cancer Institute Surveillance Epidemiology and End Results (SEER) data, the age adjusted incidence rate of lymphoma in the general US population was 22.0 per 100,000 person-years during 2000-2004. Literature review has indicated a similar rate of 22.6/100,000 PY as reported by Gelfand and Margolis⁵ in a control psoriasis population using the General Practice Research Database (GPRD) in the UK. However, the lymphoma rate was 47.7/100,000 PY in the psoriasis patient population that excluded mild cases (defined as those who had not previously received systemic therapy). Other studies have previously reported a higher rate of 56.0/100,000 PY in an older psoriasis patient population with an average age of 59, excluding cutaneous T cell lymphoma. Therefore, the data reported by Gelfand and Margolis were considered the most appropriate basis for calculation of the sample size for this registry.

Using the rate of 0.0477/100 PY from this reference as representative of patients that would be eligible for biological therapy for the treatment of psoriasis, a total of 21500 PY of observation time is needed to provide 80% power to rule out the doubling of 0.0477/100 PY with a 1-sided 95% CI, i.e., the upper bound of the one-sided confidence interval is < 0.0954/100 PY.

[figure not shown]
Using an expected patient year attrition rate of 40%, the ten-year registry of 5,000 patients will provide an expected 30,000 PY of observation. When considering the additional 1,000 patients who will be permitted to enter the registry from outside US and Canada, the ten-year registry of 6,000 patients will provide an expected 36,000 PY of observation. This will markedly exceed the number of patient-years of observation necessary to rule out the doubling of the lymphoma rate among moderate-to-severe psoriasis patients.

11.0 Final Report and Publications

[figure not shown]
At the end of the registry, a final registry report will be written. This report will contain a description of the objectives of the registry, the methodology of the registry and its results and conclusions. The completed eCRFs, questionnaires and the registry report must be treated as the confidential property of AbbVie and may not be released to unauthorized people in any form (publications or presentations) without express written approval from AbbVie. The results of this registry may be published by AbbVie or by any one of the participating physicians after agreement with AbbVie.

12.0 Completion of the Registry

The physician will conduct this registry in compliance with the protocol and all applicable regulatory and legal requirements. AbbVie may terminate this registry at any time, either in its entirety or at a site, for reasonable cause provided that written notice is submitted at a reasonable time in advance of the intended termination. The physician may also terminate the registry at their site for reasonable cause, after providing written notice to AbbVie a reasonable time in advance of the intended termination.

The end-of-registry is defined as the date of the last patient's visit in the registry or the HCP Process, whichever occurs later.

[figure not shown]

Appendix A. List of Abbreviations and Definition of Terms

Abbreviations

AE Adverse event

AESI Adverse event of special interest

AS Ankylosing spondylitis
BCC Basal cell carcinoma
CD Crohn's disease

CHF Congestive heart failure

CRO Contract Research Organization
CVA Cerebrovascular Accident

DLQI Dermatology Life Quality Index

EC Ethics Committee

eCRF Electronic case report form
EDC Electronic Data Capture

eSAE Electronic serious adverse event

EU European Union

FDA US Food and Drug Administration
GPRD General Practice Research Database

HCP Health Care Provider IgG1 Immunoglobulin

IRB Institutional Review Board

KM Kaplan Meier

MedDRA Medical Dictionary for Regulatory Activities

MI Myocardial Infarction

MTX Methotrexate

NMSC Non-melanoma skin cancer PGA Physician's Global Assessment

PRO Patient reported outcome

Ps Psoriasis

PsA Psoriatic arthritis

PUVA ultraviolet A and psoralen

PY Patient-year

RA Rheumatoid arthritis

HUMIRA® (adalimumab)
P10-023 Protocol Amendment 3
Psoriasis HUMIRA® Registry

SAE Serious adverse event

SCC Squamous cell carcinoma

SEER Surveillance Epidemiology and End Results

SIR Standardized incidence ratio

TB Tuberculosis

TNF Tumor necrosis factor

UBC United BioSource Corporation

US **United States** UVB Ultraviolet B

WPAI-SHP Work Productivity and Activity Impairment-Specific Health Problem

HUMIRA® (adalimumab)
P10-023 Protocol Amendment 3
Psoriasis HUMIRA® Registry

Appendix C. Physician Global Assessment

The Physician's Global Assessment (PGA) is a 6-point scale used to measure the severity of disease at the time of the physician's evaluation of the patient. The degree of overall lesion severity will be evaluated using the following categories:

Score	Category	Category Description
0	Clear	Plaque elevation = 0 (no elevation over normal skin) Scaling = 0 (no scale) Erythema = \pm (hyperpigmentation, pigmented macules, diffuse faint pink or red coloration)
1	Minimal	Plaque elevation = \pm (possible but difficult to ascertain whether there is a slight elevation above normal skin) Scaling = \pm (surface dryness with some white coloration) Erythema = up to moderate (up to definite red coloration)
2	Mild	Plaque elevation = slight (slight but definite elevation, typically edges are indistinct or sloped) Scaling = fine (fine scale partially or mostly covering lesions) Erythema = up to moderate (up to definite red coloration)
3	Moderate	Plaque elevation = moderate (moderate elevation with rough or sloped edges) Scaling = coarser (coarse scale covering most of all of the lesions) Erythema = moderate (definite red coloration)
4	Severe	Plaque elevation = marked (marked elevation typically with hard or sharp edges) Scaling = coarse (coarse, non tenacious scale predominates covering most or all of the lesions) Erythema = severe (very bright red coloration)
5	Very severe	Plaque elevation = very marked (very marked elevation typically with hard sharp edges) Scaling = very coarse (coarse, thick tenacious scale over most of all of the lesions; rough surface) Erythema = very severe (extreme red coloration; dusky to deep red coloration)

[figure not shown]
Note: Presented by [name], Medical Officer, Division of Dermatologic and Dental Drug Products, Center for Drug Evaluation and Research, Food and Drug Administration. Bethesda (MD): Dermatologic and Ophthalmic Advisory Committee 49th Meeting; 20 March 1998.

Appendix D. Dermatology Life Quality Index

The aim of this questionnaire is to measure how much your skin problem has affected your life OVER THE LAST WEEK. Please check one box for each question.

[figure not shown]
1.	Over the last week, how itchy, sore, painful or stinging	Very much	
	has your skin been?	A lot	
		A little	
		Not at all	
2.	Over the last week, how embarrassed or self conscious	Very much	
	have you been because of your skin?	A lot	
		A little	
		Not at all	
3.	Over the last week, how much has your skin interfered	Very much	
	with you going shopping or looking after your home or	A lot	
	yard?	A little	
		Not at all	Not relevant
4.	Over the last week, how much has your skin influenced	Very much	
	the clothes you wear?	A lot	
		A little	
		Not at all	Not relevant
5.	Over the last week, how much has your skin affected any	Very much	
	social or leisure activities?	A lot	
		A little	
		Not at all	Not relevant
6.	Over the last week, how much has your skin made it	Very much	
	difficult for you to do any sport ?	A lot	
		A little	
		Not at all	Not relevant
7.	Over the last week, has your skin prevented you from	yes	
	working or studying?	no	Not relevant
	If "No," over the last week how much has your skin been	A lot	
	a problem at work or studying?	A little	
		Not at all	
8.	Over the last week, how much has your skin created	Very much	
	problems with your partner or any of your close friends	A lot	
	or relatives?	A little	
		Not at all	Not relevant

9.	Over the last week, how much has your skin caused any sexual difficulties?	Very much A lot A little Not at all	Not relevant
10.	Over the last week, how much of a problem has the treatment for your skin been, for example by making your home messy, or by taking up time?	Very much A lot A little Not at all	Not relevant

[figure not shown]
Please check you have answered EVERY question. Thank you.

[©] AY Finlay, GK Khan, April 1992

[figure not shown]
